### Other costs

Indicate yes or no, by marking with a cross (X) in the relevant box.

	Yes	No
Participant has purchased any over-the-counter medicines or attended any private therapy sessions as a result of symptoms during the last 3 months (including herbal or complementary remedies (eg, crystals and visits to alternative practitioners)		

If yes, provide further detail below.

Medicine / preparation / herbal remedy bought or appointment with private practitioner	Total number of purchases or visits in last 3 months	Cost of each remedy or private session
1		
2		
3		
4		
5		
6		
7		

### Additional care costs

Indicate yes or no, by marking with a cross (X) in the relevant box.

	Yes	No
Participant has not incurred any additional costs as a result of symptoms such as requiring informal care		

If yes, provide further detail below.

	Type of help	Total number of visits in last 3 months	Average cost of each visit
1	Personal care (eg, washing, dressing, etc)		
2	Help in / around house (eg, cooking, cleaning)		
3	Help outside the home (eg, shopping, transport)		
4	Child care		
5	Other, please specify:		
6	Other, please specify:		

7	Other, please specify:		
----------	------------------------	--	--

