### Use of outpatient hospital services over the last 3 months

Indicate yes or no, by marking with a cross (X) in the relevant box.

	Yes	No
Participant has made any outpatient hospital visits in the last 3 months		

If yes, provide further detail below.

	Service	Total number of appointments in last 3 months
1	Accident and Emergency department	
2	Radiology department	
3	Physiotherapist	
4	Occupational Therapist	
5	Psychiatric outpatient visit	
6	Other, please specify:	

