### Use of inpatient hospital services over the last 3 months

Indicate yes or no, by marking with a cross (X) in the relevant box.

	Yes	No
Participant has made any inpatient hospital visits in the last 3 months		

If yes, provide further detail below.

	Service	Total number of admissions in last 3 months	Total number of inpatient days
1	General medical ward		
2	Psychiatric rehabilitation ward		
3	Acute psychiatric ward		
4	Other, please specify:		

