#### Any primary and community care contacts over the last 3 months

Indicate yes or no, by marking with a cross (X) in the relevant box.

	Yes	No
Participant has used any primary and community care services in the last 3 months		

If yes, provide further detail below.

	Service	Total number of contacts in last 3 months	Average duration of each attendance (minutes)
1	GP surgery		
2	GP home visit		
3	Practice nurse		
4	Community psychiatric nurse		
5	Walk-in centre		
6	Out-of-hours care		
7	Occupational therapist		
8	Social worker		

9	Advocate (eg, creative support)		
10	Home-help / home care worker		
11	Community support worker		
12	Psychiatrist		
13	Psychologist		
14	Other, please specify:		

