### Travel costs

Indicate yes or no, by marking with a cross (X) in the relevant box.

	Yes	No
Participant has incurred any travel costs associated with use of services in the last 3 months		

If yes, provide further detail below.

Location	Main method of travel (eg, private car, bus)	Cost of return trip if public transport (£XX.XX)	Number of miles round trip if private car (XX.X)	Total parking fees (£XX.XX)
1				
2				
3				
4				
5				
6				

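### The CSRI gate question on additional care costs is worded in the negative but keeps an If-yes instruction, so a literal reading skips the cost table for those who had such costs

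*Combined protocol and SAP*

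**What the plan says.** Under Additional care costs, Appendix B gives the nurse a statement with Yes and No boxes: "Participant has not incurred any additional costs as a result of symptoms such as requiring informal care". The next line is "If yes, provide further detail below". Below it is a table asking, by type of help, for the number of visits in the last 3 months and the average cost of a visit. The types are personal care, help in or around the house, help outside the home, child care and other. The form has no instruction for a No answer, and nothing elsewhere in the protocol corrects the routing.

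Section 7.4 says that the research nurse administers the CSRI. Section 7.6 schedules it at day 1, week 12 and week 24; the flow chart puts the middle one at week 6, but either way there are three. Section 3.2 names patient cost next to health and social care service cost in the secondary objective, and section 3.5 makes the outcome a change in cost from baseline to week 24.

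**The concern.** The skip instruction opens the cost table for the wrong group. If one nurse answers as printed and another answers what the form evidently means, a recorded Yes or No has no fixed meaning. An empty table may then mean either that there was no cost or that the section was skipped.

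The outcome is a within-participant change in a study without a control arm (section 4). A question read one way at baseline and another way at week 24 can therefore produce an apparent change in this component, with no comparator to offset it. Section 11.3 plans means and standard deviations by visit and gives no rule for ambiguous CSRI fields.

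**Working it through.** The documents state no figure to reproduce. The check is of wording and skip logic.

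**Comparison with the other gates in Appendix B that carry the same If-yes instruction**

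| Section of the CSRI | Gate | Direction |
|---|---|---|
| Outpatient services | "Participant has made any outpatient hospital visits in the last 3 months" | affirmative |
| Inpatient services | "Participant has made any inpatient hospital visits in the last 3 months" | affirmative |
| Primary and community care | "Participant has used any primary and community care services in the last 3 months" | affirmative |
| Travel costs | "Participant has incurred any travel costs associated with use of services in the last 3 months" | affirmative |
| Other costs | "Participant has purchased any over-the-counter medicines or attended any private therapy sessions as a result of symptoms during the last 3 months" | affirmative |
| Informal care | whether a relative, friend or similar person provides help | affirmative |
| Additional care costs | "Participant has not incurred any additional costs as a result of symptoms such as requiring informal care" | **negative** |

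The first five also state the 3-month window in the gate. The additional-care gate does not, although its table does.

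**Truth table for the additional-care gate, read literally**

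| Participant's situation | Statement is | Answer | Table |
|---|---|---|---|
| Had such costs | false | No | skipped |
| Had no such costs | true | Yes | requested, with nothing to enter |

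Both groups are misrouted. With affirmative wording, as in the travel gate, the same If-yes instruction routes both correctly.

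**Effect on the change score.** Let C0 and C24 be a participant's true additional-care cost at baseline and week 24, and suppose that a skipped table is entered as zero. The true change is C24 − C0.

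- Literal at baseline, by intent at week 24: recorded change = C24 − 0 = C24, so the error is C24 − (C24 − C0) = +C0.
- By intent at baseline, literal at week 24: recorded change = 0 − C0 = −C0, so the error is −C0 − (C24 − C0) = −C24.
- Literal at both: recorded change = 0, so the error is −(C24 − C0) and the whole component is lost.
- By intent at both: no error.

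The documents give neither the frequency of these costs nor their amount, and do not say how the gate would be read. No money value follows, and any figure would be invented.

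**Overlap with other sections.** The primary and community care table counts contacts with a home-help or home care worker and their duration, but no price paid by the participant. The informal care section records the helper's relationship, employment, time off work and weekly hours, but no payment. The travel section covers trips to services. The participant-reported cost per visit for these kinds of help, and child care, appear only in the affected table.

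**The case against.** The strongest reply is that the error is unlikely to do much harm. The form is not self-completed. A nurse reads it under a heading about costs, with a cost table directly beneath and six affirmative gates around it. A literal Yes exposes the mistake at once, because the nurse then has a table with nothing to enter. Copies go to the sponsor within 3 working days (section 12.2), and data are monitored for quality (section 13). This stands in part: it makes loss at every administration a worst case, not an expectation. It does not remove the defect. A literal No with an empty table looks the same as an intended No with no costs, and the monitoring text does not say how to tell them apart. The CSRI is not built into the electronic record, so the paper form is the source (section 12.1), and contact with the research nurse ends after week 24 (section 7.5).

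A second reply concerns scope, and it stands in full. Time off work, travel, over-the-counter medicines and private therapy, informal care and service use are collected separately and are not affected.

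The missing 3-month window in the gate is a small matter, since the table sets the period for anything that would be costed.

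**Conclusion.** The gate is wrong as written and should be corrected. The consequence is a risk of missing or inconsistently recorded data at each CSRI administration, confined to one component of patient cost. Complete loss of that component is the upper bound, and it requires a literal reading throughout. The likely size cannot be set from the documents. The primary outcome and the sample size are untouched.

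A reader might infer more than this, in four ways that the documents do not support:

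- That these costs will certainly be lost. Nurse administration and the evident intent of the form make this a risk only.
- That half of the secondary objective fails. Patient cost is one of the two cost perspectives named there, and this table is one of several parts of patient cost.
- That paid or unpaid help is recorded nowhere else. The primary care and informal care sections overlap in part, although without cost per visit.
- That the Other costs section repeats the error. Its gate is affirmative and serves only as a comparator.

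**What to change.** Delete the word *not* from the gate, add a reference to the last 3 months to match its table, and keep the If-yes instruction. No other rewording is needed; replacing the reference to informal care would change the scope of the question. Issue the corrected form before use.

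For forms already completed, keep the Yes/No answer and cross-check it against the table:

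- Table filled in: use the entries, whichever box is ticked.
- Table empty, either box ticked: query it while the participant can still be contacted; otherwise treat the component as missing. Do not assume zero. Coding from the table alone would score participants whose costs were skipped as having none, which is the bias to be avoided.

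The cost is a one-line change to the form plus any amendment notification required under section 14.9, because the CSRI is an appendix to the protocol.

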**Informal care**

*Indicate yes or no, by marking with a cross (X) in the relevant box.*

	Yes	No
Participant has someone (other than nurses or home helps), such as a family member, relative, or friend, who provides help (eg, cleaning, cooking, shopping, accompanying to appointments and social events) because of the distress caused by the participant's symptoms		

*If yes, provide further detail below.*

The relationship of the person to the participant	
--	--

	Yes	No
Person is in paid employment		

*If person is in paid employment, indicate the participant's occupational group, by marking with a cross (X) in the relevant box.*

1	Manager / administrator	
2	Professional (eg, health, teaching, legal)	
3	Clerical worker / secretary	
4	Services / sales	
5	Skilled labour / craftsmen (eg, building, electrical)	
6	Factory worker	
7	Other, please specify:	

*Indicate persons' number of hours worked each week, in hours and minutes.*

Number of hours worked each week (XX:XX)	
---	--

*Indicate duration of time person has taken off work because of ill-health of the participant in the last 3 months, by indicating numerical values in each box.*

1	Months (XX)	
2	Weeks (XX)	
3	Days (XX)	

*Indicate the length of time, on average, that the person spends each week looking after / helping the participant, by marking with a cross (X) in the relevant box.*

1	1 -5 hours per week	
2	6 – 10 hours per week	
3	11 – 20 hours per week	
4	21 – 35 hours per week	
5	36 – 50 hours per week	
6	50 or more hours per week	
7	Varies: under 20 per week	
8	Varies: more than 20 per week	
9	Other, please specify:	

**18 APPENDIX C: EQ-5D-5L**

Under each heading, please tick the ONE box that best describes your health TODAY.

**MOBILITY**

- I have no problems in walking about
- I have slight problems in walking about
- I have moderate problems in walking about
- I have severe problems in walking about
- I am unable to walk about

**SELF-CARE**

- I have no problems washing or dressing myself
- I have slight problems washing or dressing myself
- I have moderate problems washing or dressing myself
- I have severe problems washing or dressing myself
- I am unable to wash or dress myself

**USUAL ACTIVITIES** (e.g. work, study, housework, family or leisure activities)

- I have no problems doing my usual activities
- I have slight problems doing my usual activities
- I have moderate problems doing my usual activities
- I have severe problems doing my usual activities
- I am unable to do my usual activities

**PAIN / DISCOMFORT**

[figure not shown]
- I have no pain or discomfort
- I have slight pain or discomfort
- I have moderate pain or discomfort
- I have severe pain or discomfort
- I have extreme pain or discomfort

**ANXIETY / DEPRESSION**

- I am not anxious or depressed
- I am slightly anxious or depressed
- I am moderately anxious or depressed
- I am severely anxious or depressed
- I am extremely anxious or depressed

- We would like to know how good or bad your health is TODAY.
- This scale is numbered from 0 to 100.
- 100 means the best health you can imagine.  
0 means the worst health you can imagine.
- Mark an X on the scale to indicate how your health is TODAY.
- Now, please write the number you marked on the scale in the box below.

YOUR HEALTH TODAY =

People's problems sometimes affect their ability to do certain day-to-day tasks in their lives. To rate your problems look at each section and determine on the scale provided how much your problem impairs your ability to carry out the activity.

1. **WORK** - if you are retired or choose not to have a job for reasons unrelated to your problem, please tick N/A (not applicable)

0	1	2	3	4	5	6	7	8	N/A
Not at all		Slightly		Definitely		Markedly	Very severely,		
							I cannot work		

2. **HOME MANAGEMENT** – Cleaning, tidying, shopping, cooking, looking after home/children, paying bills etc

0	1	2	3	4	5	6	7	8
Not at all		Slightly		Definitely		Markedly	Very severely	

3. **SOCIAL LEISURE ACTIVITIES** - With other people, e.g. parties, pubs, outings, entertaining etc.

0	1	2	3	4	5	6	7	8
Not at all		Slightly		Definitely		Markedly	Very severely	

4. **PRIVATE LEISURE ACTIVITIES** – Done alone, e.g. reading, gardening, sewing, hobbies, walking etc.

0	1	2	3	4	5	6	7	8
Not at all		Slightly		Definitely		Markedly	Very severely	

5. **FAMILY AND RELATIONSHIPS** – Form and maintain close relationships with others including the people that I live with

0	1	2	3	4	5	6	7	8
Not at all		Slightly		Definitely		Markedly	Very severely	

**W&SAS total score**

(Data item 39 in the IAPT Data Standard )

20 APPENDIX E: PHQ-9

Over the last 2 weeks, how often have you been bothered by any of the following problems?		Not at all	Several days	More than half the days	Nearly every day
1	Little interest or pleasure in doing things	0	1	2	3
2	Feeling down, depressed, or hopeless	0	1	2	3
3	Trouble falling or staying asleep, or sleeping too much	0	1	2	3
4	Feeling tired or having little energy	0	1	2	3
5	Poor appetite or overeating	0	1	2	3
6	Feeling bad about yourself — or that you are a failure or have let yourself or your family down	0	1	2	3
7	Trouble concentrating on things, such as reading the newspaper or watching television	0	1	2	3
8	Moving or speaking so slowly that other people could have noticed? Or the opposite — being so fidgety or restless that you have been moving around a lot more than usual	0	1	2	3
9	Thoughts that you would be better off dead or of hurting yourself in some way	0	1	2	3

PHQ9 total score

(Data item 37 in the IAPT Data Standard)

21 APPENDIX F: ATHENS INSOMNIA SCALE

1. SLEEP INDUCTION (*time it takes you to fall asleep after turning-off the lights*)

0	1	2	3
No problem	Slightly delayed	Markedly delayed	Very delayed or did not sleep at all

2. AWAKENINGS DURING THE NIGHT

0	1	2	3
No problem	Minor problem	Considerable problem	Serious problem or did not sleep at all

3. FINAL AWAKENING EARLIER THAN DESIRED

0	1	2	3
Not earlier	A little earlier	Markedly earlier	Much earlier or did not sleep at all

4. TOTAL SLEEP DURATION

0	1	2	3
Sufficient	Slightly insufficient	Markedly insufficient	Very insufficient or did not sleep at all

5. OVERALL QUALITY OF SLEEP (*no matter how long you slept*)

0	1	2	3
Satisfactory	Slightly unsatisfactory	Markedly unsatisfactory	Very unsatisfactory or did not sleep at all

6. SENSE OF WELL-BEING DURING THE DAY

0	1	2	3
Normal	Slightly decreased	Markedly decreased	Very decreased

7. FUNCTIONING (PHYSICAL AND MENTAL) DURING THE DAY

0	1	2	3
Normal	Slightly decreased	Markedly decreased	Very decreased

8. SLEEPINESS DURING THE DAY

0	1	2	3
None	Mild	Considerable	Intense

THIS IS TO CERTIFY THAT THE POLICIES OF INSURANCE LISTED BELOW HAVE BEEN ISSUED TO THE INSURED NAMED ABOVE FOR THE POLICY PERIOD INDICATED. NOTWITHSTANDING ANY REQUIREMENT, TERM OR CONDITION OF ANY CONTRACT OR OTHER DOCUMENT WITH RESPECT TO WHICH THIS CERTIFICATE MAY BE ISSUED OR MAY PERTAIN, THE INSURANCE AFFORDED BY THE POLICIES DESCRIBED HEREIN IS SUBJECT TO ALL THE TERMS, EXCLUSIONS AND CONDITIONS OF SUCH POLICIES. LIMITS SHOWN MAY HAVE BEEN REDUCED BY PAID CLAIMS.

INSR LTR	TYPE OF INSURANCE	ADDL INSD	SUBR WVR	POLICY NUMBER	POLICY EFF (MM/DD/YYYY)	POLICY EXP (MM/DD/YYYY)	LIMITS
A	 COMMERCIAL GENERAL LIABILITY  CLAIMS-MADE  OCCUR  GEN'L AGGREGATE LIMIT APPLIES PER:  POLICY  PRO-JECT  LOC OTHER:			35858200	1/18/2016	1/18/2017	EACH OCCURRENCE \$1,000,000 DAMAGE TO RENTED PREMISES (Ea occurrence) \$1,000,000 MED EXP (Any one person) \$10,000 PERSONAL & ADV INJURY \$1,000,000 GENERAL AGGREGATE \$2,000,000 PRODUCTS - COMPIOP AGG \$ \$ \$
	AUTOMOBILE LIABILITY  ANY AUTO  ALL OWNED AUTOS  SCHEDULED AUTOS  HIRED AUTOS  NON-OWNED AUTOS						COMBINED SINGLE LIMIT (Ea accident) \$ BODILY INJURY (Per person) \$ BODILY INJURY (Per accident) \$ PROPERTY DAMAGE (Per accident) \$ \$
	 UMBRELLA LIAB  OCCUR  EXCESS LIAB  CLAIMS-MADE DED    RETENTION \$						EACH OCCURRENCE \$ AGGREGATE \$ \$
	WORKERS COMPENSATION AND EMPLOYERS' LIABILITY ANY PROPRIETOR/PARTNER/EXECUTIVE OFFICER/MEMBER EXCLUDED? (Mandatory in NH) if yes, describe under DESCRIPTION OF OPERATIONS below		Y/N N/A				 PER STATUTE  OTH-ER E.L. EACH ACCIDENT \$ E.L. DISEASE - EA EMPLOYEE \$ E.L. DISEASE - POLICY LIMIT \$
A	Products Liability Claims Made Form			99470671	1/18/2016	1/18/2017	See Below

DESCRIPTION OF OPERATIONS / LOCATIONS / VEHICLES (ACORD 101, Additional Remarks Schedule, may be attached if more space is required)  
 Products Liability: Products & Completed Operations Aggregate: \$2,000,000  
 Each Occurrence: \$2,000,000  
 Claims Made Deductible: \$10,000  
  
 Medical Devices  
 See Attached...

